4.3.1.4. Supplementary Analyses

The two supplementary estimands defined for the primary endpoints will also be used for the key secondary endpoints (see Section 4.2.3).

4.3.2. Secondary Endpoints

The secondary endpoints in this study are:

- Mean change in severity of moderate to severe HF from baseline to Week 4 (assessed by HFDD)
- Mean change in severity of moderate to severe HF from baseline to Week 12 (assessed by HFDD)
- Mean change in frequency of moderate to severe HF from baseline to Week 1 (assessed by HFDD)
- Mean change in frequency of moderate to severe HF from baseline over time (assessed by HFDD)

The frequency and severity of moderate to severe HF and the change as well as the relative change (%) from baseline will be summarized using descriptive statistics as described in Section 4.2.1. Further details with regards to the frequency of HF and baseline values can be found in Section 4.1.2.1.

If a participant discontinues/interrupts use of adjuvant endocrine therapy, mean change in frequency of moderate to severe HF from baseline over time will be additionally presented in presence or in absence of adjuvant endocrine therapy (by treatment group and by week). Absence of adjuvant endocrine therapy is defined similar to ICE "interruption/discontinuation of adjuvant endocrine therapy"; For participants using tamoxifen, reduction of at least 50% and for or participants using aromatase inhibitors, reduction of at least 30% of planned daily dosage taken during each particular week compared to baseline.

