# 3. Objectives, Endpoints and Estimands

Objectives and endpoints are listed in Table 3-1.

Table 3-1: Objectives and endpoints

Objectives	Endpoints
Primary	
To evaluate the efficacy of elinzanetant for the treatment of VMS caused by adjuvant endocrine therapy in women with, or at high risk for developing hormone-receptor positive breast cancer	
 
Primary endpoints
 
Mean change in frequency of moderate to severe HF from baseline to Week 4 (assessed by HFDD)
 
Mean change in frequency of moderate to severe HF from baseline to Week 12 (assessed by HFDD)
 
Secondary endpoints
 
Mean change in severity of moderate to severe HF from baseline to Week 4 (assessed by HFDD)
 
Mean change in severity of moderate to severe HF from baseline to Week 12 (assessed by HFDD)
 
Exploratory endpoints:
 
Proportion of participants with at least 50% reduction in frequency of moderate to severe HF at Week 4
 
Proportion of participants with at least 50% reduction in frequency of moderate to severe HF at Week 12
 

10 MAY 2023 Page: 22 of 97

Objectives	Endpoints
Secondary	
To evaluate the onset of efficacy of elinzanetant for the treatment of VMS caused by adjuvant endocrine therapy in women with, or at high risk for developing hormone-receptor positive breast cancer	Secondary endpoints  Mean change in frequency of moderate to severe HF from baseline to Week 1 (assessed by HFDD)  Mean change in frequency of moderate to severe HF from baseline over time (assessed by HFDD)  Exploratory endpoints:  Time to treatment response

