4.2.1. Main Analytical Approach

The main estimand to answer the clinical question of the study is described in Section 1.1.

The frequency of moderate to severe HF and the change from baseline as well as the relative change (%) from baseline will be summarized using descriptive statistics (see Section 4.1) by treatment group and by week. Descriptive table will include participants on study treatment (a participant needs to have taken at least one dose of study drug during the week to be shown in the table). Post-treatment data will be used in the model-based analysis and shown in the listing only. The change from baseline over time in the frequency of HFs will be shown using line plots for means together with 95% CIs by treatment group.

Inference about the primary endpoints will be done based on a mixed model for repeated measures (MMRM). Prior to performing modeling with the MMRM, missing data will be handled in alignment with the estimand strategies for ICEs (described in Section 1.1).

Table 4–3 provides a detailed overview of the MMRM model for the change from baseline in frequency of HF. One of the stratification factors used at randomization, population type, will not be included in the analysis model because almost all participants are in the same category.

version 3.0 Page: 30 of 87

Table 4-3: Model description

Dependent variable:	Change from baseline in frequency of moderate to severe HF at Week 1, Week 4, Week 8 and Week 12
Covariates (continuous variables):	Baseline mean daily frequency of HF
Factors (class variables):	Treatment, Week
Stratification factor (class variables):	Type of treatment of pre-existing condition at baseline (tamoxifen or aromatase inhibitor)
Interaction terms:	Baseline*Week, Treatment*Week
Covariance structure:	Unstructured (UN)
	If the convergence cannot be attained with the unstructured correlation matrix, the following alternative structures will be attempted in the specified order: autoregressive(1) (AR(1)), and compound symmetry (CS). The first structure in this list with which the model converges will be used. If AR(1) structure is used, a random subject intercept will also be included in the model. This will need to be applied for each imputed dataset.
Equation	$Y_{ijkm} = \mu + \beta x_i + t_k + p_m + v_j + (tv)_{kj} + \alpha (xv)_{ij} + s_i + \varepsilon_{ijkm}$
•	where Y_{ijkm} is the change from baseline in frequency of HF to Week j for subject i (with treatment k and type of treatment m at baseline);

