The imputation will be done using a regression model (PROC MI with MONOTONE REG) including covariates described above for each time point and using the MNAR statement to estimate the model from placebo participants only.

To impute missing data for participants randomized to placebo, using MAR assumption, the imputation will be done using a regression model including measurements from all timepoints before the time-point being imputed in addition to baseline measurement and the stratification factor (PROC MI with MONOTONE REG).

PROC MI will be run with the random seed setting SEED=21656 to produce 500 imputed datasets.

After the completion of imputation step, change from baseline values will be calculated and each imputed dataset will be analyzed using the MMRM model specified in Table 4–3 to obtain an estimate of the mean change from baseline and of the treatment effect. The results will be combined using the Rubin's rule (Rubin, 1987) to obtain an overall estimated mean change from baseline and an overall estimated treatment effect. A total of 500 multiple imputation steps will be used.

Details regarding how the ICEs will be identified and specifics regarding the reasons for the occurrence of ICE are described in Section 6.4. All the ICEs will be reviewed prior to study unblinding.

The results from the main analysis will be presented as the number of participants, estimated mean change from baseline and standard error (SE) for each treatment group at Weeks 4 and 12 as well as the estimated treatment difference (elinzanetant - placebo), SE of the difference, associated 95% CI and P-value (one-sided). A plot of the model-based estimates with SE will be provided by the treatment for Weeks 4 & 12.

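### The onset objective has no planned baseline-adjusted treatment difference at Week 1, although the primary MMRM already contains Week 1 and could report one

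*SAP*

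**What the plan says.** Protocol section 3 sets a secondary objective: "To evaluate the onset of efficacy of elinzanetant for the treatment of VMS caused by adjuvant endocrine therapy". Its secondary endpoints are the change in moderate to severe HF frequency at Week 1 and over time; time to treatment response is exploratory. Protocol 9.4.3 leaves the analysis details to the SAP.

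SAP 4.3.2 states that frequency and severity "will be summarized using descriptive statistics as described in Section 4.2.1". In 4.2.1 those statistics have three features:
- "Descriptive table will include participants on study treatment", meaning at least one dose taken in the week concerned.
- "Post-treatment data will be used in the model-based analysis and shown in the listing only".
- The change in frequency over time "will be shown using line plots for means together with 95% CIs by treatment group".

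The primary model in SAP Table 4-3 has as its response "Change from baseline in frequency of moderate to severe HF at Week 1, Week 4, Week 8 and Week 12". It includes baseline, adjuvant therapy type, and baseline-by-week and treatment-by-week interactions. Section 4.2.1 also imputes missing Week 1 and Week 8 values. The results to be shown are the "estimated mean change from baseline and standard error (SE) for each treatment group at Weeks 4 and 12", together with the treatment difference, its SE, 95% CI and one-sided p-value. The ESTIMATE statements and the model-based plot likewise cover Weeks 4 and 12 only.

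Two general rules apply. SAP 2.1 and protocol 9.1 make every endpoint outside the four-test hierarchy descriptive. SAP 4.1.1 rules out imputation for secondary endpoints unless otherwise specified.

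**The concern.** A placebo-controlled trial that names speed of onset as an objective should say how far apart the arms are at the first scheduled week, and how precisely. As written, the reader gets two by-arm means from women on treatment, each with its own interval, and must judge the difference by eye. Those means are not adjusted for baseline frequency or for the stratification factor, and the estimate does not follow the treatment-policy estimand used at Weeks 4 and 12. A comparison of all randomised women under that estimand can be had from a model the sponsor will fit anyway.

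At stake is the quality of the evidence on one secondary objective. The primary and key secondary conclusions are not affected.

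**Working it through.** **1. The plan's own figures.** Inputs from SAP section 5 and protocol 9.2: 243 and 122 evaluable women, one-sided alpha 0.025, SD 3.632 (Week 4) and 4.29 (Week 12). Noncentral t power with 243 + 122 − 2 = 363 degrees of freedom gives, for differences of 1.0, 1.5 and 2.0:
- Week 4: 69.67%, 96.01% and 99.86% (stated 69.67%, 96.01% and >99.9%).
- Week 12: 55.38%, 88.16% and 98.71% (stated the same).

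The stated figures reproduce, apart from a rounding-level gap in the >99.9% entry. The point does not rest on them, but the SDs are used in step 3.

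**2. Is the Week 1 difference available from the specified model?** In the Table 4-3 equation, take the elinzanetant minus placebo mean at Week 1 for the same baseline value and therapy type. The intercept, baseline term, therapy-type term, week term and baseline-by-week term cancel. What remains is the treatment main effect difference plus the Week 1 treatment-by-week difference. In the form of the existing ESTIMATE statements, the coefficients are 1 −1 for treatment and 1 0 0 0 −1 0 0 0 for treatment-by-week. A rank check on the fixed-effects design confirmed that this contrast is estimable, as are those for Weeks 4, 8 and 12. For Week 8 the interaction coefficients are 0 0 1 0 0 0 −1 0.

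The LSMEANS statement in Table 4-3 already requests differences for all treatment-by-week cells, so SAS would compute the Week 1 difference in each imputed dataset. The ODS OUTPUT line saves the LSMeans and Estimates tables but no Diffs table, so the Week 1 difference is neither carried forward for pooling nor named among the results.

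**3. Likely precision (illustrative).** The documents give no Week 1 SD and no correlation between baseline and change, so both are assumed. The half-width is 1.96 × SD × √(1 − ρ²) × √(1/n₁ + 1/n₂).

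√(1/243 + 1/122) = 0.1110 and √(1/270 + 1/135) = 0.1054.

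| SD (assumed) | ρ (assumed) | 243/122 | 270/135 |
|---|---|---|---|
| 3.0 | 0 | 0.65 | 0.62 |
| 3.0 | 0.5 | 0.57 | 0.54 |
| 3.632 | 0 | 0.79 | 0.75 |
| 3.632 | 0.5 | 0.68 | 0.65 |
| 4.29 | 0 | 0.93 | 0.89 |
| 4.29 | 0.5 | 0.81 | 0.77 |

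The range is 0.54 to 0.93 HF/day. The gain from adjustment depends wholly on ρ: at 0.5 the factor is √(1 − 0.25) = 0.866, about 13% narrower; at 0 there is no gain.

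**4. How selected is the Week 1 table?** Week 1 is Days 2 to 8 (SAP 4.1.2.1), the first dose is supervised at the baseline visit (protocol 6.1), and one dose in the week is enough for inclusion. A treated woman drops out on adherence grounds only if she takes nothing in that week. With 10% drop-out assumed over the first three months, few should do so.

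**The case against.** The strongest reply is that descriptive reporting is a deliberate choice, stated consistently in protocol 9.1 and SAP 2.1, and that no section promises a model for these endpoints. That stands: the plan neither contradicts itself nor is unworkable. But a difference with a confidence interval, labelled as outside the hierarchy, spends no alpha and leaves H1 to H4 as they are.

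A second reply is that onset is described in other ways. This is also true. Besides the table there are line plots with by-arm 95% CIs, and SAP 4.4.1 adds a Kaplan-Meier time to response with CIs, under treatment policy and censored at study drop-out. The same section plans cumulative response curves at Weeks 4 and 12. A reader might infer that onset is judged solely from two on-treatment means with no interval of any kind; the documents do not support that. What is missing is narrower: a between-arm difference, adjusted for baseline, with its own interval.

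A third reply is that table specifications are in separate documents (SAP section 1), so the Week 1 difference may be displayed after all. That cannot be ruled out, but the SAP text on reported results names Weeks 4 and 12 only.

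A reader might also infer that adherence selection distorts the Week 1 result. Step 4 of the working makes that unlikely to be material. Selection could matter more for severity at Week 12, where post-treatment values reach only the listing, but the documents give no basis for sizing it.

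**Conclusion.** The point holds as a modest improvement. For Week 1 frequency the plan offers by-arm description only, so the onset objective lacks a planned baseline-adjusted difference and interval, although the model specified for the primary analysis can supply both. This finding rests on the SAP text and the estimability check and needs no assumption about the data.

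The half-width of 0.54 to 0.93 HF/day does rest on assumptions: an SD of 3.0 to 4.29, a baseline-to-change correlation of 0 to 0.5, and between 243/122 and 270/135 women. It shows roughly how precise the extra result would be. It is no evidence of bias or of a changed conclusion.

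It would be tempting to say the same of severity. There the case is weaker. No model is specified for severity, so nothing already fitted can be reported. The endpoint definition also differs between periods: baseline severity counts moderate and severe HF only, whereas on-treatment severity includes mild HF, with HF-free days set to 0. A model would give a comparison between arms but would not remove that mismatch.

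**What to change.** In SAP 4.2.1 and 4.3.2:
- Add ESTIMATE lines for Weeks 1 and 8, or save the Diffs table from the existing LSMEANS statement.
- Pool these by Rubin's rule over the same 500 imputed datasets as the primary analysis, and state this as the exception to the no-imputation rule in 4.1.1.
- Report the treatment difference with its 95% CI, labelled as outside the multiplicity hierarchy. The documents do not give the unblinding date; if the addition comes after it, label the result post hoc. The sponsor has already used SAP supplements to add analyses, so a route exists.

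Optionally, fit an analogous baseline-adjusted model to severity at Weeks 4 and 12 using all collected data, with a note on the differing baseline and on-treatment definitions.

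The cost is a few output lines, plus one further model if severity is included. Sample size, alpha and the confirmatory sequence do not change. The drawback is that the added results are nominal only and must not be presented as confirmatory.

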4.4. Exploratory Endpoints Analysis

For all exploratory endpoints, the ICEs will be handled according to the treatment policy. No missing data imputation is planned for these endpoints.

version 3.0 Page: 45 of 87

4.4.1. HFDD related exploratory endpoints

The following exploratory endpoints based on the HFDD will be analyzed by descriptive statistical methods as described in Section 4.1 by treatment group.

- Proportion of participants with at least 50% reduction in frequency of moderate to severe HF at week 4
- Proportion of participants with at least 50% reduction in frequency of moderate to severe HF at week 12
- Time to treatment response
- Mean change in frequency of mild, moderate, and severe HF from baseline over time (assessed by HFDD)
- Mean change in frequency of nighttime awakenings from baseline over time (assessed by HFDD)
- Mean change in proportion of days with participants rating of "quite a bit" or "very much" sleep disturbances experienced due to HF from baseline over time (assessed by HFDD).

The proportion of participants with at least 50 % reduction in frequency of moderate to severe HF at week 4 and 12 will be calculated as the proportion of participants whose baseline value for the frequency of moderate to severe HF is reduced by \geq 50 % at week 4 and 12, respectively.

A graphical summary with % change (0 to 100) in the frequency and severity of moderate to severe HF from baseline on the x-axis and proportion of participants achieving this reduction on the y-axis, by treatment group, for week 4 and 12 will also be provided. Similarly, a graphical summary with absolute change in the frequency and severity of moderate to severe HF from baseline on the x-axis and proportion of participants achieving this reduction on the y-axis, by treatment group, for week 4 and 12 will also be produced.

To assess the treatment response, threshold value for 50% reduction from baseline of the frequency of moderate to severe HF will be considered. The time to first occurrence (i.e., the first week after baseline) of a reduction of the baseline value by 50% will be analyzed. If the required reduction by week 12 is not observed, the participant will be censored at week 12. Similarly, participants that drop out of the study before achieving the required reduction, will be censored at the time of dropping out (i.e., at the last evaluable week, defined as a week with at least 5 days of diary data, before dropping out). Kaplan-Meier estimates of the time to treatment response including a 95% confidence interval (calculated based on a normal approximation and using the Greenwood formula for the standard deviation) and cumulative incidence plots based on the Kaplan-Meier estimator will be presented by treatment group. Furthermore, the proportion of treatment responders will be summarized by treatment group. In addition, the proportion of treatment responders will be presented at Week 26 and at Week 50.

The mean change in frequency of mild, moderate, and severe HF from baseline will be calculated similar to the mean change in frequency of moderate to severe HF described in Section 4.1.2.1, but will also include mild HF in the calculation. Specifically, the baseline value of the frequency of mild, moderate, and severe HF will be calculated by aggregating the available days during the 14 days prior to start of treatment to a mean daily frequency as (total number of mild, moderate, and severe HF during the 14 days prior to start of treatment) /

version 3.0 Page: 46 of 87

(total number of available days with data). As per inclusion criteria 8 (see protocol), at least 11 days will be available for the derivation of the baseline value. Similarly, the frequency of mild, moderate, and severe HF for each week during the treatment period will be calculated using the available data during that particular week and aggregated to a mean daily frequency as (total number of mild, moderate, and severe HF during that week) / (total number of available days with data during that week). In case data is missing for more than 2 days within a week, the value for that week will be set to missing and no imputation of missing values will be performed. The mean change from baseline will then be calculated as the difference in the mean daily frequency of mild, moderate, and severe HF for a given week from the corresponding baseline value.

Summary statistics for the frequency of mild, moderate, and severe HFs as well as the absolute change from baseline will be presented by week and by treatment group. The change from baseline over time in the frequency of mild, moderate, and severe HFs will be shown using line plots by treatment group.

The mean change in frequency of nighttime awakenings from baseline over time is based on the number of nighttime awakenings during the previous night that is being assessed every morning as part of the HFDD. The baseline value of the nighttime awakenings will be calculated by averaging the nighttime awakenings from the available days during the 14 days prior to start of treatment to a mean daily frequency as (total number of nighttime awakenings during the 14 days prior to start of treatment) / (total number of available days with morning data). Similarly, the frequency of nighttime awakenings for each week during the treatment period will be calculated using the available data during that particular week and averaged to a mean daily frequency as (total number of nighttime awakenings during that week) / (total number of available days with morning data during that week). In case morning data is missing for more than 2 days within a week, the value for that week will be set to missing and no imputation of missing values will be performed. The mean change from baseline will then be calculated as the difference in the mean daily frequency of nighttime awakening for a given week from the corresponding baseline value. A graphical summary (i.e. cumulative distribution function) with absolute change (0 to 100) in the frequency of nighttime awakenings from baseline on the x-axis and proportion of participants achieving this reduction on the y-axis, by treatment group, for week 4 and 12 will also be provided.

Summary statistics for the frequency of nighttime awakenings as well as the absolute change from baseline will be presented by week and by treatment group. The change from baseline over time in the frequency of nighttime awakenings will be shown using line plots for means together with 95% CIs by treatment group.

Sleep disturbances due to HF are assessed every morning as part of the HFDD. Participants provide a rating of their sleep disturbances due to HF in the previous night as

- 'not at all'
- 'a little bit'
- 'somewhat'
- 'quite a bit'
- 'very much'

version 3.0 Page: 47 of 87

To calculate the mean change in proportion of days with 'quite a bit' or 'very much' sleep disturbance due to HF, the number of days with participants having reported 'quite a bit' or 'very much' sleep disturbance will be used. The baseline value of the proportion of days with 'quite a bit' or 'very much' sleep disturbances due to HF will be calculated based on the available days during the 14 days prior to start of treatment as (number of days with sleep disturbance due to HF rated as 'quite a bit' or 'very much')/ (total number of available days with morning data). The on-treatment value for the sleep disturbances due to HF for each week will be calculated using the available data during that particular week as (number of days with sleep disturbance due to HF rated as 'quite a bit' or 'very much' during that week) / (total number of available days with morning data during that week). In case morning data is missing for more than 2 days within a week, the value for that week will be set to missing and no imputation of missing values will be performed. Mean change in proportion of days with participants having reported 'quite a bit' or 'very much' sleep disturbance due to HF from baseline will then be calculated as the difference in the mean sleep disturbance value for a given week from the corresponding baseline value.

Summary statistics for the proportion of days with participants having reported 'quite a bit' or 'very much' sleep disturbance due to HF as well as the absolute change from baseline will be presented by week and by treatment group. The change from baseline over time of the proportion of days with participants having reported 'quite a bit' or 'very much' sleep disturbance due to HF will be shown using line plots for means together with 95% CIs by treatment group.

